#### **Analyses**

Mixed effects models will evaluate whether treatment fidelity, treatment feasibility, or treatment acceptability differ significantly between MBCT-T and MBCT-V. Alpha will be set at 0.05 for all analyses.

To evaluate differences in fidelity, a multi-level linear mixed effects model will evaluate differences between MBCT-T and MBCT-V on the MBCT-TACS (72 sessions nested in 6 treatment groups). Treatment site will be included as a covariate. Repeated measures will be taken into account using session-level random effects.

To evaluate differences in feasibility and acceptability, two separate multi-level linear mixed effects model will be used to evaluate differences between MBCT-T and MBCT-V on Treatment Session Adherence and the CSQ-8 (96 participants nested in 6 treatment groups). Treatment site will be included as a covariate. Clusters

Version date: 3/8/2022

by group membership will be taken into account using random effects. Power for Aim 2. Using SDs and ICCs derived from preliminary data, with an n = 96 sessions and n = 96 participants, we have at least a power of .90 to detect the clinically important differences (CIDs) pre-specified in the decision rules for treatment fidelity (MBCT-TACS CID = 0.2 points; power > .99), treatment feasibility (Treatment Session Adherence CID = 15%; power > .99) and treatment acceptability (CSQ-8 CID = 5 points; power = .91).

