## Clinically Important Differences (CIDs) and statistical significance

If minimum benchmarks (see above) for all arms are met, we will move forward with **both MBCT-T** and **MBCT-V** vs. **EUC** in a fully-powered Phase III clinical trial **so long as neither version of MBCT is superior to the other based on the following analyses:** 

- 1) **MBCT-T/V Treatment fidelity**: MBCT-TACS is at least ≥0.2 points higher in the superior compared to the inferior arm, and this difference is statistically significant.
- 2) **MBCT-T/V Treatment feasibility** is at least 15% higher in the superior arm compared to the inferior arm, and this difference is statistically significant.
- 3) **MBCT-T/V Treatment acceptability** is at least 5 points higher in the superior arm compared to the inferior arm, and this difference is statistically significant.
- 4) MBCT-T/V Clinical utility: 50% responder rate for the HDI (10-point change from M0-M3) and the QIDS-SR (5-point change from M0-M3). No significance testing between MBCT-T and MBCT-V will be conducted for this outcome.

If one of the above criteria is met (i.e., one treatment meets threshold for being superior to the other), we will select this treatment to move forward with further testing in a fully-powered Phase III trial.

If we observe mixed results (e.g., MBCT-T is superior on feasibility but MBCT-V is superior on clinical utility) we will utilize results from secondary outcomes to further explore differences between the MBCT-T and MBCT-V treatment arms to inform the selection of treatment arms for the Phase III trial.

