#### **Planned Secondary Analyses**

Descriptive statistics (means and standard deviations or ns and %s) will be calculated for all secondary outcomes. Secondary outcomes for Aim 1 will be assessed via: 1) daily diary (Homework Adherence during intervention, Headache Frequency, Pain Intensity); 2) monthly survey (Headache Disability Inventory, QIDS-SR (depressive symptoms), MBCT Home Practice inventory, Migraine-Specific Quality of Life, Co-occurring Treatment Tracking, Adverse Events); or administrative data (Survey Completeness, Diary Completeness and Attrition). For secondary outcomes evaluated with daily diary, multi-level mixed effects models will evaluate changes in the outcomes at the day-level across treatment arm (MBCT-T vs. MBCT-V vs. EUC). Repeated measures (day) within person will be taken into account by using person-level random effects. Clusters by group membership will be taken into account using a random effect. Treatment site will be included as a covariate. For secondary outcomes evaluated with monthly surveys, multi-level mixed effects models will evaluate changes in the outcomes at the month-level across treatment arm (MBCT-T vs. MBCT-V vs. EUC). Repeated measures (month) within person will be taken into account by using person-level random effects. Treatment site will be included as a covariate.

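### The Aim 2 model text gives 72 sessions and 6 groups where the design has 96 and 12, and two models name no treatment-group effect

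*Combined protocol and SAP*

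**What the plan says.** Section 9.1, Analyses (Aim 2), describes the fidelity model as multi-level and as comparing the two MBCT arms "on the MBCT-TACS (72 sessions nested in 6 treatment groups". The attendance and CSQ-8 models are described with "96 participants nested in 6 treatment groups". The power statement that closes the same text works "with an n = 96 sessions and n = 96 participants", and says that SDs and ICCs came from preliminary data without giving them.

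On random effects:

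- **Fidelity:** "Repeated measures will be taken into account using session-level random effects". Site is a covariate. No group effect is named.
- **Attendance and CSQ-8:** a random effect for group membership is named.
- **Daily diary (Planned Secondary Analyses):** person-level effects, and then "Clusters by group membership will be taken into account using a random effect".
- **Monthly surveys (same section; HDI, QIDS-SR, MSQ and others):** "Repeated measures (month) within person will be taken into account by using person-level random effects". Site is a covariate. No group effect is named.

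The Phase III selection rule for fidelity asks for a score at least 0.2 "points higher in the superior compared to the inferior arm, and this difference is statistically significant". For the HDI and QIDS-SR responder criterion, "No significance testing between MBCT-T and MBCT-V will be conducted for this outcome".

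**The concern.** There are two separate problems.

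The first is that the counts in the model text do not fit the design described elsewhere, or the power statement in the same section. A wrong count in a sentence does not change an analysis of the real data. It does leave open which cluster structure was used for the stated powers, and the number 6 appears in both model descriptions.

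The second is the missing group term. Sessions of one group share an instructor and a set of participants, and participants of one group share all their sessions. If outcomes correlate within groups, a model without a group term treats correlated observations as independent, so its standard errors are too small. A session-level effect does not repair this. With one score per session it cannot be told apart from the residual. With two or more raters (Section 6.1.3) it captures agreement between raters on one session, not similarity between sessions of one group.

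At stake are the fidelity significance test, which is a named condition of the selection rule, and the uncertainty around the Month 0 to Month 3 slopes. Section 7.2.1.5 says those slopes will supply the effect sizes for the Phase III sample size.

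**Working it through.** **1. Counts.** Inputs: 3 sites (9.1, Aim 1A); 2 groups per MBCT arm per site (5.6; 9.1, Sample Size Justification and Power for Aim 1); groups of 8 patients with 8 weekly sessions (7.2.1.3.1).

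- Groups: 3 x 2 x 2 = 12.
- Sessions: 12 x 8 = 96, which is 48 per arm and 32 per site, as Aim 1A states.
- Participants: 12 x 8 = 96.

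The model text fails every reading: 6 x 8 = 48 sessions, not 72; 72/6 = 12 sessions per group, not 8; 72/8 = 9 groups; 96/6 = 16 participants per group, not 8.

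**2. The stated powers.** They cannot be reproduced, because no SD or ICC is given. Working backwards with 48 per arm, two-sided alpha .05 and a normal approximation, SD = CID / (1.960 + z_power) / sqrt(2/48):

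- MBCT-TACS, power .99: 0.2 / (1.960 + 2.326) / 0.2041 = 0.229.
- CSQ-8, power .91: 5 / (1.960 + 1.341) / 0.2041 = 7.42, clustering included.

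The cluster count matters here. If .91 was computed for 12 groups of 8, the same inputs with 6 groups of 16 (design effect 1 + 15 ICC instead of 1 + 7 ICC) give .890, .826, .777 and .725 at ICC .01, .05, .10 and .20.

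**3. Fidelity test without a group term.** The large-sample formula is 2[1 - Phi(1.96 / sqrt(1 + 7 ICC))]. The simulation used 12 groups x 8 sessions with arm and site in the model, and 200,000 null trials per ICC. The group-level test uses the 12 group means on 12 - 4 = 8 df.

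| Assumed ICC | Formula | Simulated, no group term | Group-level test |
|---|---|---|---|
| .05 | .092 | .095 | .050 |
| .10 | .133 | .138 | .050 |
| .20 | .206 | .217 | .049 |

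**4. Full selection rule (significant and at least 0.2 points), no true difference.**

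| Assumed ICC | SD .23, no group term | SD .23, group-level test | SD .25, no group term |
|---|---|---|---|
| .05 | .0002 | .0002 | .0007 |
| .10 | .0010 | .0010 | .0026 |
| .20 | .0059 | .0054 | .0113 |

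An SD of .25 is the largest possible if every session scores between 2.5 and 3.0. If the stated power above .99 already includes clustering, the SD is at most .229 / sqrt(1 + 7 ICC) = .197, .175 or .148. A chance difference of 0.2 or more then has probability .000018.

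**5. Monthly slopes without a group term.** Simulation of 144 persons with a site covariate, 200,000 runs per setting.

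| Share of slope variance between groups | MBCT-T vs MBCT-V | One MBCT arm vs EUC |
|---|---|---|
| 0 | .050 | .049 |
| .02 | .066 | .058 |
| .05 | .091 | .071 |
| .10 | .135 | .095 |

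The first row covers groups that differ only by a constant. In balanced data the group term changes the uncertainty of a slope, not its estimate.

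**The case against.** The count error is beyond dispute. The case against the rest is one of reading and weight.

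- **Fidelity wording.** The model is called multi-level, sessions are nested in groups, and repeated measures most naturally means sessions within a group. ICCs are said to have been used for power. A group level may well be intended. This stands as a reading, but an analyst has to fit what is written, and the level is not written.
- **Consequence for decisions.** No decision rests on the fidelity p-value alone, and step 4 shows that the group term hardly moves the selection rule. HDI and QIDS-SR enter selection as untested responder rates. This stands in full.
- **Assumed inputs.** No ICC, SD or slope share is in the documents, and the site covariate may absorb part of any instructor effect. This also stands: the inflation figures are conditional.
- **Group size.** Section 7.1.6 lets a group start with 6 to 8 participants, so groups of 8 are planned, not guaranteed. That changes group size, but produces neither 6 groups nor 72 sessions.
- **Remedy.** Small-sample degrees of freedom and a singular-fit fallback go beyond correcting the text. The fallback returns some trials to the model without a group term. That is fair, and the fix below separates the necessary from the advisable.

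None of this explains why the monthly-survey model lacks a term that the diary model, in the same section and on the same participants, includes.

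**Conclusion.** The concern holds. The figures of 72 sessions and 6 groups contradict the design and the power statement; the correct planned figures are 96 sessions and 96 participants in 12 groups. The monthly-survey model omits the group term outright. The fidelity model leaves it unstated.

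Fitted as written, both models give intervals that are too narrow whenever the relevant outcome is correlated within groups: for fidelity, any within-group ICC above zero; for the slopes, only if groups differ in change over time. The size depends on assumed ICCs and slope shares. The effect on Phase III arm selection through fidelity is small, and the Aim 1 benchmarks are untouched. The stated powers are not shown to be wrong; the text does not let a reader tell which structure they used.

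**What to change.** **Needed.**

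- State 96 sessions and 96 participants in 12 planned treatment groups in the Aim 2 model descriptions.
- Name a treatment-group random intercept in the fidelity model. Keep a session effect only if several ratings of one session enter the model.
- Add a treatment-group effect to the monthly-survey models for the MBCT arms only, since EUC modules are taken individually (7.2.1.3.2), with group-by-time where it can be estimated.
- Confirm that the three Aim 2 powers were computed for 12 groups with the group effect, restate them if not, and report the SDs and ICCs.

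**Advisable.**

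- Use small-sample degrees of freedom (Kenward-Roger) for the linear models.
- Pre-specify what happens if the fit is singular: drop group-by-time first, then the group term. For fidelity, dropping the group term when its variance is estimated as zero held type I error at .043, .048 and .050 at ICC .05, .10 and .20 (400,000 runs). The two-step version for the monthly models has not been checked in the same way.

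**Cost.** SAP wording and a power check.

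- Where the group term is kept, fidelity intervals widen by (2.306 / 1.986) x sqrt(1 + 7 ICC) = 1.35, 1.51 and 1.80 at ICC .05, .10 and .20, which reflects the real uncertainty. The group variance would be estimated as zero in about 31%, 17% and 5% of trials.
- If the stated powers are large-sample figures for 12 groups with ICCs included, an 8-df test lowers .99 for fidelity to about .96 and .91 for CSQ-8 to about .82. The CSQ-8 loss comes from the degrees of freedom, since that model already names the group effect. It would fall below the plan's own floor of .90.

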## 6.1.3 Procedures for Training Interventionalists and Monitoring Intervention Fidelity

In accordance with recommendations in the field, the clinician will be required to have a minimum of master's level training in clinical psychology and a regular mindfulness practice of at least two years. The clinician will be licensed or will be practicing under a licensed clinician. Fidelity will be ensured by using treatment manuals, session fidelity checklists, and weekly supervision of session audio recordings to minimize drift. Treatment fidelity will be evaluated by two or more independent raters, with a minimum of 85% inter-rater reliability, using the MBCT-TACS scale.

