#### 9.1 Description of Statistical Methods

Basic descriptive statistics (e.g., means and standard deviations, frequencies and percentages, or medians and interguartile ranges) for variables of interest will be computed. Distributions of each variable will be examined. Graphical approaches will be used to further explore the data where appropriate. Differences in demographics and clinical characteristics at baseline will be evaluated across the three treatment arms. No missing data is anticipated for treatment fidelity or treatment feasibility primary outcomes. For the CSQ-8, missing data will be singly-imputed as the lowest possible score on the CSQ-8, indicating dissatisfaction with the treatment. For clinical utility responder rates, missing data will be singly-imputed as non-response to treatment. For secondary outcome analysis, missing data will be estimated as part of the mixed models procedures. Primary analyses will not be adjusted. Any significant differences on demographic variables between treatment groups will be included as covariates in secondary adjusted models of the secondary analyses described below. SPSS, SAS and R will be used to conduct the analyses. All tests will be two-tailed with alpha set at 0.05.

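### The fidelity model that can help choose the Phase III arm names only a session-level random effect, so as written it leaves sessions of the same treatment group independent; a treatment-group intercept should be named.

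*Combined protocol and SAP*

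**What the plan says.** Section 9.1, Aim 2, Analyses, plans a multi-level linear mixed model comparing MBCT-T with MBCT-V "on the MBCT-TACS (72 sessions nested in 6 treatment groups", with site as a covariate. One sentence covers the random part: "Repeated measures will be taken into account using session-level random effects". The next paragraph, on attendance and CSQ-8, handles clusters differently: they "by group membership will be taken into account using random effects".

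Under Planned Secondary Analyses the level named is the cluster and not the repeated unit: "Repeated measures (day) within person will be taken into account by using person-level random effects". Section 6.1.3 adds that "Treatment fidelity will be evaluated by two or more independent raters", so a session may carry more than one score.

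The result feeds a selection rule. One MBCT version counts as superior on fidelity if "MBCT-TACS is at least ≥0.2 points higher in the superior compared to the inferior arm, and this difference is statistically significant". If one superiority criterion is met, "we will select this treatment to move forward with further testing in a fully-powered Phase III trial". On significance, Section 9.1 states: "All tests will be two-tailed with alpha set at 0.05". Power for the 0.2-point fidelity difference is given as above .99, using SDs and ICCs from preliminary data that are not reported.

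**The concern.** Sessions of one treatment group share the same members and, presumably, the same facilitator. Their fidelity scores are therefore likely to be alike, and the group is the unit within which sessions repeat. A random effect for session has only two possible roles. With several raters it captures their agreement on one session. With one score per session it cannot be separated from the residual. In neither case does it let the group means vary beyond session noise.

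The arm comparison would then run on 96 sessions as if independent, although the documents describe 12 groups. The decision rule asks for significance as well as size, as a check against chance. An anti-conservative test weakens that check in a comparison that can decide which treatment goes to Phase III.

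**Working it through.** **Inputs.** Two groups per MBCT arm per site (Sample Size Justification for Aim 1) and three sites give 3 × 2 × 2 = 12 groups. Eight weekly sessions each (Section 7.2.1.3.1) give 96 sessions, 48 per arm, which agrees with Aim 1A. The fidelity model sentence instead gives 72 sessions in 6 groups, or 12 per group. Alpha is 0.05 two-sided and the threshold is 0.2 points. SD and ICC are not given, so ICCs of 0.1, 0.3 and 0.5 are assumed.

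**Step 1: the stated power.** It cannot be reproduced without an SD, but it bounds the SD. For power .99 with 48 independent sessions per arm:

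SD ≤ 0.2 / [(1.960 + 2.326) × √(2/48)] = 0.229.

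Dividing by √(1 + 7 × ICC) gives 0.175 at ICC 0.1 and 0.130 at ICC 0.3. With 72 independent sessions (36 per arm) the cap is 0.198.

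**Step 2: type I error as written.** In balanced data, a session intercept gives the same arm test as treating session means as independent. The true variance of the arm difference is larger by DE = 1 + (m − 1) × ICC. The approximate error is 2 × [1 − Φ(1.96/√DE)].

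| 12 groups of 8 | ICC 0.1 | ICC 0.3 | ICC 0.5 |
|---|---|---|---|
| DE | 1.7 | 3.1 | 4.5 |
| Understatement of SE, √DE | 1.30 | 1.76 | 2.12 |
| Approximate type I error | 13% | 27% | 36% |
| Simulated, session as unit | 14% | 29% | 39% |
| Simulated, group as unit (8 df) | 5% | 5% | 5% |

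The simulation adjusts for site and has no true difference (20,000 runs per setting). It exceeds the approximation because the session-level residual variance is itself too small. At ICC 0.5 its expectation is [84 × 0.5 + 64 × (0.5 + 0.5/8)] / 92 = 78/92 = 0.85 of the total variance. With 6 groups of 12, the error runs from 12% to 52% for ICC 0.05 to 0.5. At ICC 0 there is no inflation.

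**Step 3: chance selection under the full rule.** Take SD 0.229. The session-level test declares significance from about 1.96 × 0.229 × √(2/48) = 0.092 points. Any difference that reaches 0.2 therefore also passes the test, and the threshold does the work. With SE = 0.229 × √(DE × 2/n), the chance is about 2 × [1 − Φ(0.2/SE)].

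| SD 0.229 | ICC 0.1 | ICC 0.3 | ICC 0.5 |
|---|---|---|---|
| 12 groups of 8: SE | 0.061 | 0.082 | 0.099 |
| Approximation | 0.1% | 1.5% | 4.4% |
| Simulated, session-level test | 0.1% | 1.6% | 4.3% |
| Simulated, group-level test | 0.1% | 1.3% | 2.5% |
| 6 groups of 12: DE | 2.1 | 4.3 | 6.5 |
| SE | 0.078 | 0.112 | 0.138 |
| Approximation | 1.1% | 7.4% | 14.6% |
| Simulated, session-level test | 1.0% | 7.1% | 14.7% |
| Simulated, group-level test | 0.3% | 1.7% | 2.6% |

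If the SD is instead held to the 72-session cap of 0.198, the 6-group approximation is 0.3%, 3.9% and 9.3%.

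**Step 4: larger SDs (12 groups of 8, ICC 0.05 to 0.5).** Chance selection is 0.4% to 13% at SD 0.3. At SD 0.5 it is 8% to 34%, against 4% to 5% with a group-level test.

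**The case against.** The strongest reply is that a group effect was intended. The paragraph calls the model multi-level, nests sessions in groups, and says ICCs entered the power calculation. That is possible, and a reader who infers that the plan certainly ignores groups goes further than the text. But the sentence that specifies the random part names another level, and the power statement does not say which level its ICCs refer to. Two analysts could fit different models and both claim to follow the plan.

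The second reply is that little follows from it. A reader might infer that the significance condition gives almost no protection against choosing an arm by chance. The documents do not support that. Power above .99 implies an SD of at most 0.229. If it already carries a group-level ICC, the chance of a 0.2-point difference under the null is about 0.002%. The scale runs from 0 to 3, and all sessions in preliminary testing met the benchmark, which also suggests a small SD. With 12 groups the threshold then keeps chance selection below 5% even at ICC 0.5. This stands for 12 groups and small SDs. It does not cover the model sentence's own 6 groups or a larger SD in the trial.

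Other limits also stand. Fidelity does not always decide alone: all arms must first meet the benchmarks, and mixed results go to secondary outcomes. Who teaches which groups is not stated, so if one facilitator taught both arms at a site, the site covariate would absorb part of the correlation. Nor is the fidelity model the only one without a group term, since the monthly-survey models name none. It is the only one of the three mixed models in the selection rule that lacks it.

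**Conclusion.** The point holds as a misspecified or at best incomplete random part in a model used for selection. Followed literally, the significance test has a type I error of about 14%, 29% and 39% at ICC 0.1, 0.3 and 0.5 with 12 groups, instead of 5%.

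The effect on arm selection is smaller and depends on quantities the documents omit. At SD 0.229 it is slight with 12 groups: at ICC 0.5, 4.3% against 2.5% with a group-level test. With 6 groups it is material, at 14.7% against 2.6%. It grows with the SD. All these figures rest on assumed ICCs, balanced data and an SD inferred from the stated power. The defect merits correction because the rule is pre-specified and the change is small; it does not show that the wrong arm is likely to be chosen.

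**What to change.** In Section 9.1, Aim 2, Analyses, replace the random-effects sentence for fidelity with wording to this effect: a random intercept for treatment group, with sessions nested in group; a session random effect only where a session has scores from more than one rater; and arm tested with Kenward-Roger or Satterthwaite degrees of freedom.

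Reconcile 72 sessions in 6 groups with the 96 sessions in 12 groups that follow from Section 7.2.1.3.1, Aim 1A and the Aim 1 sample size text. Restate the fidelity power under the new model, with its SD, its ICC and the level of that ICC.

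The cost is about one sentence and one recalculation. The stated power may become less favourable: at an assumed SD of 0.20 with 12 groups, group-level power for 0.2 points is .989, .907, .684 and .528 at ICC 0, 0.1, 0.3 and 0.5.

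### The Aim 2 power figures (.91 to >.99) describe the significance test only; each two-part superiority criterion is met at most about half the time when the true difference equals the CID

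*Combined protocol and SAP*

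**What the plan says.** The decision rules are in section 9.1, under Clinically Important Differences (CIDs) and statistical significance. One MBCT version is superior to the other in any of these cases:

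- Fidelity: "MBCT-TACS is at least ≥0.2 points higher in the superior compared to the inferior arm, and this difference is statistically significant".
- Feasibility (session attendance): it "is at least 15% higher in the superior arm compared to the inferior arm, and this difference is statistically significant".
- Acceptability (CSQ-8): it "is at least 5 points higher in the superior arm compared to the inferior arm, and this difference is statistically significant".
- Clinical utility: a responder-rate criterion on the HDI and QIDS-SR, with no significance test between the two versions.

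The criteria are alternatives: "If one of the above criteria is met (i.e., one treatment meets threshold for being superior to the other), we will select this treatment". If every arm meets its benchmarks and neither version is superior, both go into Phase III.

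The power statement is at the end of Analyses in the same section. It says that "we have at least a power of .90 to detect the clinically important differences (CIDs) pre-specified in the decision rules", and then gives "MBCT-TACS CID = 0.2 points; power > .99", "Treatment Session Adherence CID = 15%; power > .99" and .91 for a 5-point CSQ-8 difference. It refers to preliminary SDs and ICCs without printing them. On the test itself, section 9.1 says: "All tests will be two-tailed with alpha set at 0.05".

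**The concern.** The power statement names the decision rules and sets the true difference at the same value that the observed difference has to reach. A reader will take .91 or >.99 as the chance that a criterion identifies a version that is worse by exactly the CID. A test of zero difference can have that power. A criterion that also needs the estimate to reach the CID cannot.

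Aim 2 consists of these rules, and they determine the arms of the Phase III trial. If the power figures are read as properties of the rules, the chance of missing a CID-sized difference on one domain looks like 9% (CSQ-8) or under 1% (attendance, fidelity). On that criterion it is about 50%. The document gives no operating characteristics for the two-part criteria.

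**Working it through.** **Inputs from section 9.1.** Two-sided alpha .05. CIDs of 0.2 MBCT-TACS points, 15 percentage points of attendance (reading the 15% as an absolute difference) and 5 CSQ-8 points. Stated powers of >.99, >.99 and .91. Ninety-six sessions and 96 participants, so 48 per MBCT arm.

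**The plan's own figures.** They cannot be reproduced directly, because the SDs and ICCs are not printed. The standard error (SE) each one implies can be back-solved from CID/SE = z(.975) + z(power):

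- CSQ-8: 5/(1.960 + 1.341) = 5/3.301, so SE = 1.515.
- Attendance: 15/(1.960 + 2.326) = 15/4.286, so SE is at most 3.50 percentage points.
- MBCT-TACS: 0.2/4.286, so SE is at most 0.0467.

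The last two are upper bounds, because the stated power is above .99. For the CSQ-8, SE 1.515 with 48 per arm is an effective SD of 1.515/√(2/48) = 7.42. Putting that into a two-mean power formula returns .91. This shows consistency; it does not verify the figure independently.

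**Which condition binds.** Significance is reached at 1.96 × SE:

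- CSQ-8: 1.96 × 1.515 = 2.97 points, 59% of the CID.
- Attendance: at most 1.96 × 3.50 = 6.9 percentage points, 46% of the CID.
- MBCT-TACS: at most 1.96 × 0.0467 = 0.091 points, 46% of the CID.

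At the planned precision, the observed-CID condition is the binding one.

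**Probability of meeting one criterion when the true difference equals the CID.** P(estimate ≥ CID) = 1 − Φ((CID − CID)/SE) = 1 − Φ(0) = .50. SE cancels, so neither n, SD nor ICC changes the result. If the SE were so large that 1.96 × SE exceeded the CID, significance would bind and the probability would be below .50.

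Two variants were checked:

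- With a t reference and SEs tuned to power .91 or .99, the result is .48 to .50 for 2 to 94 degrees of freedom.
- Simulating the CSQ-8 with 12 groups of 8 or 6 groups of 16, ICC .01 to .10 and power tuned to about .91, it is .49 to .50.

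**Away from the CID (CSQ-8, SE 1.515).** The probability is Φ((true − 5)/1.515):

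- True difference 4: Φ(−0.66) = .25.
- True difference 5: .50.
- True difference 6: Φ(0.66) = .75.

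**True difference needed for a given probability.** This is CID + z × SE:

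- CSQ-8, 80%: 5 + 0.842 × 1.515 = 6.3 points.
- CSQ-8, 90%: 5 + 1.282 × 1.515 = 6.9 points.
- Attendance, 90%: at most 15 + 1.282 × 3.50 = 19.5 percentage points.
- MBCT-TACS, 90%: at most 0.2 + 1.282 × 0.0467 = 0.26 points.

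**At least one of criteria 1 to 3.** If one domain differs by exactly its CID and the others do not differ, the chance stays about .50. If all three differ by exactly their CIDs in the same direction, and the estimates are independent (an assumption), it is 1 − .5³ = .875.

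**The case against.** The best defence is that power to detect a difference conventionally means the power of a test at that true difference. The sentence follows a description of mixed models that ask whether the arms differ significantly. On that reading nothing has been miscalculated. This stands: a reader might infer that .91 and >.99 are wrong, but without the SDs and ICCs that cannot be shown. It does not rescue the wording, because the sentence ties the figures to decision rules that are not decided by significance alone.

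It can also be said that about 50% at the cut-off is inherent in any observed-difference threshold, and that a demanding standard for dropping an arm is reasonable in a pilot. This stands too, and is a reason to keep the rule. With the implied SE, the chance of a 5-point observed CSQ-8 difference in either direction when there is no true difference is only about .001.

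Three further readings go beyond the documents:

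- *The Aim 2 rule as a whole has 50% power.* Any one of four criteria selects an arm. The chance that at least one is met rises when several domains differ, and the clinical-utility criterion is a further route with no stated power.
- *A clinically inferior version would go into Phase III half the time.* The default of advancing both applies only if all arms meet their benchmarks. As an illustration, CSQ-8 means of 28 and 23 differ by 5, but the weaker arm fails the requirement of more than 24 whether or not the superiority criterion is met.
- *The significance condition is redundant.* That holds only at SEs back-solved from unprinted inputs. Realised SEs may be larger. Dropouts without a CSQ-8 are scored 8, which may widen the spread, and the fidelity model lists 72 sessions where the power statement uses 96. The condition protects against more variability than planned.

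Finally, the threshold could be read as applying to the true difference. The criteria attach significance to the same difference, so the observed or model-estimated difference is the natural reading.

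**Conclusion.** The power statement is wrong as a description of the pre-specified criteria. At a true difference equal to the CID, each of criteria 1 to 3 taken alone is met with probability of at most about .50, against the stated .91 and >.99. The gap is 41 percentage points for the CSQ-8 and at least 49 for the other two.

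The .50 needs only an unbiased, roughly symmetric estimate and the observed-difference reading of the threshold; it does not depend on the missing SDs and ICCs. The 80% and 90% points do depend on SEs back-solved from the stated powers under a normal approximation. The conclusion is per criterion. It does not extend to the combined rule, to how often an inferior version would advance, or to the accuracy of the significance-test power.

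**What to change.** In Power for Aim 2, label the three figures as power of the significance test only, and print the SDs and ICCs behind them. Add the probability of meeting each two-part criterion at true differences below, at and above the CID: about .50 at the CID, with the 80% and 90% points derived above, recalculated from the actual preliminary inputs. Also give the probability that at least one of criteria 1 to 3 is met under stated scenarios, for example one domain differing and all three differing.

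Leave the decision rule unchanged. Replacing the observed-CID condition with significance plus a 95% confidence interval that includes or exceeds the CID would not work for the CSQ-8. The interval includes 5 once the estimate reaches 5 − 1.96 × 1.515 = 2.03, but significance already needs 2.97. That rule reduces to significance alone and loses the 5-point requirement.

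The cost is a few sentences of protocol text and a less favourable stated figure. No extra participants are needed.
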